
Drs. [name] and [name] have previously collaborated in a study investigating salivary cortisol levels in IPV victims⁴⁵. Using similar methodology as proposed here in which 4 salivary samples were collected over a 1-hour period (see C2), the cortisol awakening response was investigated in a sample of 52 shelter residents. Results suggested that IPV-related PTSD severity was associated with significantly greater cortisol output the first hour after waking. Thus, pilot data support the use of cortisol response within S-IPV victims as well as the ability of the research team to successfully collect multiple saliva samples from shelter residents.

C2. Study Design: To test our hypotheses that HOPE will significantly reduce severity of IPV-related PTSD and re-abuse in S-IPV victims compared to PCT, we plan to enroll 186 residents of battered women shelters with IPV-related PTSD into a prospective randomized controlled trial comparing HOPE to a attention-matched control condition (i.e., PCT). Residents of battered women shelters meeting study eligibility (see below) will be randomized into one of the two study arms. Participants will be offered 16 sessions of therapy (see Figure 1), either HOPE or PCT, beginning while women are in shelter (0-10 sessions) and continuing until 3-months post-shelter (6-16 sessions). The number of sessions attended within the shelter environment is dependent on participants' length of shelter stay, with a maximum of 10 sessions in shelter. Participants will then complete the remaining 6-16 sessions of HOPE outside of shelter. Therapy sessions will occur in shelter or another convenient, safe, and confidential location. Participants will be blinded to whether or not they received the investigative treatment or control condition. Blinded outcome assessments will be administered 1-week post-shelter treatment, 1-week post-shelter, and 1-week, 6-months, and 1-year-post-treatment.

Figure 1. Proposed model for delivery of treatment and assessment of outcome.

*Participants who are still in shelter after their 10th session will participate in monthly booster sessions.

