Rationale for the study design: Pilot work with HOPE has determined that HOPE is associated with improved outcomes relative to standard shelter services alone. Given that there is no other existing PTSD treatment appropriate for this population that could serve as a comparison condition the next logical stage in evaluating the efficacy of HOPE is to determine if HOPE offers improvement over a credible control condition that controls for the nonspecific components of therapy. PCT (see appendix) is a problem-focused, supportive therapy that is frequently used as an attention-matched control condition in clinical trials of PTSD^{46, 47}. PCT does not incorporate any of the hypothesized active ingredients of HOPE (e.g., cognitive-restructuring, acquisition of new behavioral skills, safety planning, access to resources, and empowerment strategies), but does provide psychoeducation on PTSD. Further, PCT is also clinically realistic, as many practitioners incorporate this approach into their standard practice⁴⁸. Therefore, we chose to compare HOPE to PCT, in order to determine if components specific to HOPE are responsible for observed effects, rather than nonspecific factors consistent with supportive therapy. [name] who has established expertise in PCT⁴⁶ will assist in adapting PCT to meet the needs of the proposed study, as well as in the training and supervision procedures for the PCT arm of this study.

Sample and recruitment: Participants will be 186 women recruited over 27 months from six battered women's shelters in five different counties within a 55 mile radius of the University of Akron (see letters of support) and randomized either to receive HOPE ($n = 93$) or PCT ($n = 93$). Both treatments will start while women are residents of shelter and extend after they leave shelter. Given that the length of shelter stay is variable and outside of experimenter control, session frequency will be individualized based on length of shelter stay. We are currently employing this model in our work with HOPE with success (see C1). Participants in both treatment conditions will receive up to ten individual sessions while in shelter, and 16 sessions in for up

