Adequacy of Sample Size: Optimal Design 2.0 Software⁵³ was used to conduct power analyses for hierarchical linear modeling (see C3) of treatment effects. An alpha level of .05 was chosen for each of the primary hypotheses. Given that our pilot research has found medium effect size (ES) on the higher end of the continuum for PTSD severity and medium ES for re-abuse severity (see C1), a more conservative medium ES (delta = .60; which is on the lower end of the continuum of medium effect sizes) was assumed in an effort to account for the potential for reduced effects in the current study. We also assumed an ES variability of .07 across the 6 shelters where recruitment will occur. An ES variance of .07 corresponds to a standard deviation of approximately .2, which for ES = .60 reflects substantial variation in treatment ES across shelters. Thus, we are powering the study to be able to detect a medium ES, even if there is substantial ES variability across shelters. Additional assumptions for the power analysis included a proportion of explained variance by the blocking variable (i.e., shelter) of .1 and a proportion of explained variance by the level 1 covariate (i.e., baseline PTSD or violence severity), of .3. There is little literature on which to base estimates of these two parameters for the proposed study, but these parameters have relatively little effect on sample size requirements given the specified ES, ES variability, and number of shelters. For example, the most extreme value of 0 (instead of .1) for the proportion of explained variance by the blocking variable would only increase the necessary sample size by 2 per shelter. Also, even an extreme value of .1 (instead of .3) for proportion of explained variance by the baseline level of the outcome variable would only increase the necessary sample size by 5 per shelter. Using the parameter estimates specified above and a desired power of .80, results of the

power analysis indicated that 25 participants were required per shelter for a total N of 150. In our pilot research we had retention rates of 81-95% (see C1). Thus, assuming the more conservative attrition rate of approximately 20%, we would need 31 participants per shelter, for a total of 186 participants to achieve a power of .80 to detect medium-sized treatment effects for our primary outcomes.

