Noncompleters: In general, women who do not attend at least 8 sessions (i.e., $\frac{1}{2}$ of sessions, as prior work with HOPE finds treatment effects when participants attend approximately 50% of sessions) will be considered noncompleters. Women will not be discontinued from the treatment protocol for noncompliance. All women will be invited to continue treatment and follow-up assessments. Given the unpredictable and demanding lives of our target group, most of whom are low-income, flexibility is important to make the treatment accessible to them (see assessment and retention sections for how we will address barriers in scheduling appointments).

Clinical Deterioration/Suicidal Risk. To increase safety, participants will be removed from the treatment phase of the trial as a result of clinical deterioration or suicidal risk (see E1 for procedures, assessment & definitions). Participants will remain in the research sample, be followed, and included in all analyses.

Therapists: Therapists for the intervention will consist of 4 community therapists who have been rated as qualified practitioners of HOPE or PCT (see below). Licensed, Master level (psychology, social work, counseling, or other related field) therapists will be recruited from the two local community mental health agencies who have served as our primary referral sources for this population throughout our pilot work (and thus are representative of the types of agencies most likely to treat victims of IPV who seek shelter). Each therapist will be required to have a minimum of two years of experience working with trauma populations, as well as training and experience in CBT interventions. Potential therapists will be interviewed by the PI. The interview will include questions about their training in trauma and CBT. Role-plays will also be used to assess the adequacy of their training and their ability to learn the proposed treatment protocols.

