The four community therapists will be trained in either the conduct of HOPE or PCT. We chose to train therapists in only one treatment modality in order to eliminate the risk of contamination in the control group and assure that HOPE is compared to a true attention-matched control condition. Therapists will be randomly assigned to deliver either HOPE or PCT. Existing systematic training programs (certification processes) in the conduct of HOPE and PCT that have been implemented in prior research will be used for the proposed study. As in prior research utilizing community therapists⁵⁵ each therapist will have two closely supervised training cases prior to taking on participants enrolled in the randomized trial. For both HOPE and PCT, the overall training objectives are for therapists to understand and learn to perform the intervention, to avoid using techniques or materials not part of the intervention, to ensure the use of relatively consistent procedures across different participants, and to deliver the intervention in a culturally sensitive manner. HOPE training (see training manual in appendix) includes a two-day workshop on HOPE conducted by [name], that includes lectures on IPV and PTSD, the theoretical conceptualization of HOPE, and the structure of, techniques used in, and conduct of HOPE sessions. The training program will also teach strategies for maintaining the therapist and participant safety when conducting HOPE sessions post-shelter, as well as procedures for managing emergency situations. Role-plays of appropriate and effective as well as faulty strategies to conduct the sessions, and strategies to manage participants whom may have difficulty in comprehending or utilizing the techniques will be included in the workshop. PCT training will also include a two-day workshop on PCT conducted by [name]. Drs. [name] and [name] will work closely with [name] in adapting the existing didactic training program for this study. Therapists will be trained in general issues in working with IPV victims, including strategies for managing emergencies. The workshop will include a description of the theoretical rationale behind PCT, as well as specific PCT strategies. Training will also be provided outlining specific strategies that are not to be used as a part of PCT (e.g., cognitive-restructuring, skills training, and other overlapping components with HOPE). Role-plays of appropriate and effective as well as faulty strategies to conduct the sessions, and strategies to manage more difficult clients will be included in the workshop.

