LIFE	X		X	X		X		X		X
CSQ						X		X		X

Note. MSSSI administered at any time point if participant endorses SI. CAPS administered at mid-tx assessments if DTS increases 50%. *Only the substance module of SCID-I/P administered at follow-up.

Adherence and Competence: All therapy sessions will be recorded. [name], a consultant on this project who is well-trained in treatment of IPV-related PTSD, as well as in HOPE, serving as a therapist in our pilot work with HOPE will rate adherence and competence of the delivery of 5% of randomly selected HOPE and PCT sessions (i.e., 74 HOPE and 74 PCT sessions). She will also participate in the PCT training with the study therapists and consult with [name] in order to develop competence in rating PCT sessions. HOPE and PCT have established adherence and competence scales used in prior research (see appendix)^{37, 46}.

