Mediators and Moderators of Treatment Response: Exploratory regression analyses will be conducted to evaluate whether treatment effects are mediated by degree of empowerment, effective use of resources, and trauma-related cognitions, as well s to determine if participants' PTSD symptoms post-treatment mediate severity of re-abuse over follow-up. The statistical significance of the mediated, or indirect effects, will be tested using bootstrapping methods which under most conditions, provide the most powerful way to obtain confidence intervals for mediated effects⁹⁰. Regression analyses will also be used to evaluate potential moderators of treatment response, that is, to determine for whom a relationship between intervention and treatment outcome exists. Interaction terms (i.e., treatment group X potential moderator) will be tested for minority status and for baseline measures of IPV severity, PTSD severity, attentional biases to trauma cues and physiological reactivity to trauma cues.

Treatment Integrity. Descriptive analyses will be run for the adherence and competence scales for both HOPE and PCT. Bivariate correlational analyses will be run to determine if degree of adherence and competence relates to outcome. Any cases where a session was found to have inadequate adherence and/or competence will not be used in analyses.

Figure 2.

	Year 1	Year 2	Year 3	Year 4
Start up	█			
Recruitment		█	█	
Intervention		█	█	
Follow up		█	█	█
Evaluation				█
Dissemination				█

D. Timeline and Milestones

Study time line for four-year project:

Start up period (Y1, Months 1-6): Includes program refinement, institutional review board approval, therapist, RA, project coordinator, rater, and assessment training, and database development. Recruitment period (Y 1 Mo 6- Y3 Mo 9). Intervention (Y1 Month 6 – Y3 Mo 12). Follow up (Y1 Month 9 Y 4 mo 11). Evaluation (Y5 mo 6-12): The data safety monitoring committee will meet bi-annually to evaluate the safety of the intervention program and to review blinded analysis and any adverse events. The analysis will begin after outcome assessments are complete and the data are cleaned. Dissemination (Y5 mo 6-12): Manuscript preparation, community and national presentations, focus groups with shelter and community staff and other stakeholders to assist in developing a dissemination plan to inform a future dissemination study of HOPE.

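### The planned bivariate correlations of adherence and competence with outcome leave out the baseline score, so they can be biased if delivery ratings track baseline severity, and they lose precision if they do not.

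*Combined protocol and SAP*

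**What the plan says.** Section C3, Treatment Integrity, plans descriptive summaries of the adherence and competence scales in both arms and then: "Bivariate correlational analyses will be run to determine if degree of adherence and competence relates to outcome". It names no covariate. It does not say which outcome or time point is meant, whether the outcome is a raw follow-up or a change score, or whether the arms are pooled. The next sentence removes from analyses any case with a session found inadequate in adherence or competence.

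The ratings come from a sample of sessions. Under Adherence and Competence in C2, a consultant will "rate adherence and competence of the delivery of 5% of randomly selected HOPE and PCT sessions (i.e., 74 HOPE and 74 PCT sessions").

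The baseline score is treated as an important predictor elsewhere. Adequacy of Sample Size in C2 assumes "a proportion of explained variance by the level 1 covariate (i.e., baseline PTSD or violence severity), of .3". Table 1 shows that CAPS, DTS and CTS-2 are all collected at baseline.

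On therapists, C2 says "Therapists for the intervention will consist of 4 community therapists", and each is trained in only one of the two treatments. C3 plans a separate preliminary look at therapist effects on attendance, attrition and primary outcomes. The optional covariates in C3 are described for the hierarchical linear models of treatment effect. Neither provision is attached to the integrity correlations.

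**The concern.** Randomisation protects the comparison of HOPE with PCT. It does not protect a comparison, within an arm, of women whose sessions were rated high with women whose sessions were rated low. Anything related to both the rating and the outcome enters the correlation. Baseline severity is the obvious candidate, because the plan itself expects it to account for nearly a third of outcome variance. Whether it is also related to the rating is unknown, and a bivariate correlation cannot allow for it.

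At stake is the reading of a supporting analysis. A correlation produced by baseline severity could be reported as a relation between delivery quality and outcome, or a real relation could be masked. Even with no such link, predictable outcome variance stays in the error term of an analysis that is already small. The same section uses regression for mediators and moderators, so a covariate-adjusted analysis is within the plan's existing methods.

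**Working it through.** **Inputs from the documents.** 93 women per arm; 16 sessions offered to each; 5% of sessions rated; baseline score explaining .3 of outcome variance. The .05 level is stated for the primary hypotheses; I take it as two-sided and apply it here.

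**Assumed, not in the documents.** A correlation between adherence and baseline severity of -.1 to -.3; no true effect of adherence; normally distributed scores.

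**Step 1: the plan's own figure.** 93 × 16 × 0.05 = 74.4 sessions per arm, which agrees with the stated 74.

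**Step 2: how many women are rated.** If 74 sessions are drawn at random from 93 × 16 = 1,488, the expected number of women with at least one rated session is 93 × [1 − C(1472, 74)/C(1488, 74)] ≈ 52 per arm, or 74/52 ≈ 1.4 rated sessions each. This takes all 16 sessions as attended. About 50 women per arm is a fair working size.

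**Step 3: correlation with a raw follow-up score under no true effect.** The baseline-outcome correlation is √.3 = .548. The expected adherence-outcome correlation is the assumed adherence-baseline correlation times .548:
- at -.1: -.055
- at -.2: -.110
- at -.3: -.164

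**Step 4: false-positive rate.** By Fisher's z with n = 52, the shift is atanh(|r|) × √49, and the rejection rate is 1 − Φ(1.960 − shift) + Φ(−1.960 − shift). At -.3: atanh(.164) × 7 = 1.16, so the rate is 1 − Φ(.80) + Φ(−3.12) ≈ .21.

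| Assumed adherence-baseline r | Expected r with outcome | False-positive rate |
|---|---|---|
| 0 | 0 | .05 |
| -.1 | -.055 | .07 |
| -.2 | -.110 | .12 |
| -.3 | -.164 | .21 |

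Simulation at n = 50 (6,000 runs per setting) gives .065, .116 and .201 for the last three rows. With the baseline score in the model, the rate is .048 to .052.

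**Step 5: direction with a change score.** Take change as follow-up minus baseline, with equal variances. The expected correlation is −r(adherence, baseline) × √[(1 − .548)/2] = −r × .476. At -.2 and -.3 this is about +.10 and +.14. Lower adherence would then go with more improvement, the opposite sign to Step 3.

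**Step 6: effect of removing inadequate cases.** If the lowest 20% of adherence ratings are dropped (an assumed share), the simulated rates in Step 4 at -.2 and -.3 fall to about .08 and .11.

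**Step 7: precision without confounding.** Adjusting for baseline multiplies residual variance by about .7, so the standard error of the slope falls by about 1 − √.7 = 16%. For an assumed standardised slope of .35 at n = 50, simulated power rises from .66 to .79.

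**The case against.** The strongest reply is that this is a descriptive integrity check on sparse ratings. It asks only whether delivery relates to outcome, and it touches no primary, secondary, mediator or moderator analysis. A simple correlation is a defensible first look. That stands as to importance: adjustment is a refinement. It does not make the unadjusted version better when the baseline score is already collected.

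Four stronger readings are tempting, and the documents do not support them.

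- **Harder cases will appear as an effect of poor delivery.** The HOPE workshop does cover "strategies to manage participants whom may have difficulty in comprehending or utilizing the techniques". That passage says nothing about symptom severity or about adherence falling with such women. Therapist training procedures points the other way, with a scripted manual, weekly tape review and replacement of therapists who do not achieve good adherence. Step 5 also shows that the sign depends on an outcome definition that the plan leaves open.
- **A false result would flow into training or dissemination.** The Dissemination section builds that plan from focus groups. No passage routes these correlations into it.
- **A therapist term must be in the main model.** With four therapists, each delivering one treatment, an even split (not stated) gives about two per arm. Competence may differ mainly between them, so a fixed therapist effect could remove much of the variation of interest.
- **Adjustment makes the slope valid.** The return to about .05 in Step 4 holds because baseline was the only confounder simulated. Difficulties that arise during treatment, such as new abuse or crises, could still be related to both rating and outcome.

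**Conclusion.** The point holds as a minor improvement to a supporting analysis. From the documents alone it is certain that the planned analysis has no baseline term, that the plan expects baseline to explain .3 of outcome variance, and that adherence is not randomised. It follows that the correlation can be biased if ratings are related to severity, and that precision is lost if they are not: a standard error about 16% smaller is available.

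The size of any bias is not established. The range of .07 to .21 rests on an assumed adherence-baseline correlation of -.1 to -.3, raw follow-up scores and about 50 rated women per arm. At zero correlation there is no inflation, and removing inadequate cases would shrink it. That removal is a separate issue which baseline adjustment does not address.

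**What to change.** Replace the bivariate correlations in C3, Treatment Integrity, with the following. Within each arm, regress the follow-up outcome on the woman's mean adherence rating, and separately on her mean competence rating, with the baseline value of that outcome as covariate. Name the outcome and the time point. Report the slope with its confidence interval, and label the analysis exploratory and non-causal. As a sensitivity analysis, repeat it with a fixed therapist term and show both slopes side by side.

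The cost is a change of SAP wording and one degree of freedom in the main model. The sensitivity model uses one more degree of freedom if an arm has two therapists, and more if a therapist is replaced. No new data are needed, since the baseline measures are in Table 1 and the treating therapist is known.

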Therapist training procedures: Procedures for training and monitoring therapists will mirror those used in prior research utilizing community therapists⁵⁵. [name], will assist in refining the training and monitoring protocols of community level therapists. To optimize the rapid acquisition and maintenance of therapist skills, supervision will initially be intensive, with supervision being titrated to skill level so that it becomes less intensive as therapists acquire more experience. [name] will oversee weekly group supervision sessions with all community therapists. [name] will provide individual supervision titrated to skill level to each of the community therapists. [name] and the project coordinator will review therapists' audiotapes on a weekly basis and provide feedback during individual and group supervision sessions. The therapists will be closely monitored for competence and adherence throughout the study and if at any time a therapist does not achieve good adherence, the therapist will be replaced with another therapist who will have received the training and completed the certification process. If a therapist has problems delivering the treatment, then data associated

with this therapist will not be included in any analyses. We are confident that we will be able to successfully train community therapists in HOPE, as we have successfully trained master-level graduate students in HOPE in our prior research. Further, we are using rigorous training procedures that have been successful in prior clinical trials with PTSD treatments⁵⁵. Finally, HOPE is a very structured treatment with a detailed and well scripted manual, leaving very little room for therapists to veer from standardized treatment procedures.

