Prior to conducting analyses for the main project aims, a series of routine procedures will be conducted to ensure the data accuracy/adequacy. We will also examine the distribution of our key variables for skewness, variability, missing data, and outliers. Data will be transformed to achieve normality if needed. At this time, we will also assess the effectiveness of the randomization procedures. If between-group differences exist, relevant variables will be included as covariates in outcome analyses. We will also explore whether contamination is a significant issue by comparing members of the control groups reporting they were exposed to specific HOPE content to those who were not exposed to determine if such exposure impacts outcome, and control for exposure in analyses below if necessary. Although only a small percentage of participants in our pilot work reported initiation of a new medication (3.3%), change in dose or type of ongoing medications (3.3%), or cessation of a medication (5%), we will also explore whether medication changes during treatment impacted outcome, and control for medication changes in analyses if necessary (see below). Additionally, we will preliminarily investigate therapist effects on attendance, attrition, and primary outcomes and use this data to inform future research with HOPE that will more directly assess therapist effects. Finally, pattern mixture methods^{74, 75} will be used to assess the ignorability of missingness in all outcome analyses described below. All analyses will include an intent-to-treat analysis (using data from all randomized participants) and a minimal attendance analysis (i.e., attending at least $\frac{1}{2}$ of sessions). For intent-to-treat analyses, missing data will be handled using multiple imputation with an expectation maximization algorithm.

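### Dropping cases with an inadequately rated session takes poor delivery out of the adherence–outcome correlations or, on the other reading, breaks the intent-to-treat commitment

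*Combined protocol and SAP*

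**What the plan says.** Four places bear on this.

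- **C3, Treatment Integrity.** After descriptive analyses of the scales, the plan states: "Bivariate correlational analyses will be run to determine if degree of adherence and competence relates to outcome". The next sentence is: "Any cases where a session was found to have inadequate adherence and/or competence will not be used in analyses". It does not say which analyses are meant.
- **C2, Therapist training procedures.** If a therapist has trouble delivering the treatment, the data linked "with this therapist will not be included in any analyses".
- **C2, Adherence and Competence.** A consultant "will rate adherence and competence of the delivery of 5% of randomly selected HOPE and PCT sessions", given as 74 sessions in each arm.
- **C3, opening paragraph.** "All analyses will include an intent-to-treat analysis (using data from all randomized participants"), alongside a minimal attendance analysis. No exception is made for delivery quality.

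**The concern.** The correlation asks whether women whose treatment was delivered less well did worse. The exclusion rule selects on that same predictor and discards its low end. Under a linear relation, the remaining spread of adherence is smaller, so the correlation shrinks and fewer cases are left to estimate it. If outcome worsens only below the adequacy threshold, the retained cases cannot show it at all.

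The rule is also uneven. It can act only on a woman who has a rated session, and ratings cover a small random sample. Of two women with equally poor delivery, one may be removed and the other kept because of which recordings were drawn.

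At stake are the plan's stated test of delivery quality against outcome and, if the rule reaches the outcome models, the randomized comparison itself.

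**Working it through.** **1. The plan's own figure.** Inputs: 93 women per arm (C2, Sample and recruitment), 16 sessions offered (C2, Study Design) and 5% rated (C2, Adherence and Competence). 93 × 16 = 1,488 sessions per arm, and 0.05 × 1,488 = 74.4. The stated 74 is reproduced.

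**2. Women with any rated session.** With random selection, the chance that at least one of a woman's 16 sessions is drawn is 1 − 0.95^16 = 0.56. Then 0.56 × 93 ≈ 52 women per arm. The chance rises with attendance: at 8 sessions it is 1 − 0.95^8 = 0.34. This takes an inadequate finding to come from the 5% rating. C2 also describes weekly audiotape review for supervision, but ties no rating to it.

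**3. Shrinkage of the correlation.** Assumptions, none of them from the documents: a normal adherence score with one value per woman, a linear relation with outcome, true r = .30, and a share q of rated cases inadequate, taken as the lowest q of the scores.

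- Cut point a = Φ⁻¹(q), and h = φ(a)/(1 − q).
- Ratio of the SD after deletion to the SD before: u = √(1 + a·h − h²).
- Correlation after deletion: r′ = r·u / √(1 − r² + r²u²).

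For q = 0.10: a = −1.28, h = 0.195 and u = √(1 − 0.250 − 0.038) = 0.844. Then r′ = 0.253/√(0.91 + 0.064) = 0.256.

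**4. Power.** Fisher z, two-sided 0.05: power ≈ Φ(atanh(r)·√(n − 3) − 1.96).

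- All 52 kept: Φ(0.3095 × 7 − 1.96) = Φ(0.207) = .58.
- q = 0.10, 47 kept: Φ(0.262 × 6.63 − 1.96) = Φ(−0.22) = .41.

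| Share inadequate (assumed) | SD ratio u | r after deletion | Women kept per arm | Power, one arm | Power, arms pooled (n = 104 before deletion) |
|---|---|---|---|---|---|
| 0% | 1.00 | .30 | 52 | .58 | .88 |
| 5% | 0.90 | .27 | 49 | .47 | .78 |
| 10% | 0.84 | .26 | 47 | .41 | .71 |
| 20% | 0.76 | .23 | 42 | .32 | .57 |
| 30% | 0.70 | .22 | 36 | .24 | .45 |

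For a true r of .50, the correlation falls to .46, .44, .40 and .38 at the same four shares, and one-arm power falls from .97 to .92, .88, .76 and .62.

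**5. The other reading, set side by side.** Suppose the rule covers the outcome models. The opening paragraph of C3 includes everyone randomized. Treatment Integrity removes women by how their sessions went after randomization. The therapist rule in C2 does the same for a therapist's whole caseload, in any analysis. These cannot all be followed. The documents do not allow this effect to be sized.

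**The case against.** **Scope.** The exclusion may have been meant only for the treatment comparison, leaving the correlations whole. That reading is available and the text does not rule it out. It does not rescue the sentence, because the rule then conflicts with the intent-to-treat statement. One reading or the other applies, and the wording has to change under both.

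**Size.** C2 describes therapist qualification, two supervised training cases, certification, ongoing monitoring and replacement, so the inadequate share may be small. At 5% the correlation moves only from .30 to .27. At 10% the loss of .04 is well inside the standard error of about (1 − .30²)/√51 = .13. This stands: unless poor delivery is common, the small rated sample limits the correlation more than the truncation does. A regression slope would also survive truncation under linearity, but the plan specifies correlations.

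**Stronger readings that the documents do not support.**

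- A reader might treat the 74 rated sessions per arm as 74 observations and quote higher power. Outcomes belong to women, and about 52 per arm would have a rating.
- A reader might lower coverage to 48% by using the pilot mean of 12.7 attended sessions (1 − 0.95^12.7). That does not fit the stated 74. If 74 of 93 × 12.7 = 1,181 sessions are rated, the rate is 6.3%, and coverage is again about 56%.
- A reader might infer that a null correlation would feed the dissemination plan as proof of robust delivery. The Dissemination section of C2 builds that plan from focus groups and does not mention this correlation.
- Nor is this the only look at delivery: C3 also plans a preliminary study of therapist effects on attendance, attrition and primary outcomes.

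**Conclusion.** The point holds as a fault in a stated rule. As written, the correlations exclude the poor-delivery cases they need and are biased toward zero. Read the other way, the rule contradicts the analysis of all randomized participants. In both cases, who is removed depends partly on a 5% random draw that reaches about 56% of women.

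The direction of the bias follows from the linear model and needs no assumed figure; its size does. With true r = .30, 52 women per arm and 5% to 30% inadequate, r falls to between .27 and .22 and one-arm power from .58 to between .47 and .24. The model is approximate: the 74 rated sessions spread over about 52 women, so some women have more than one rating, and the rule removes a case for failing on either scale. The correlation is not a primary analysis. The intent-to-treat conflict is the more consequential part if the rule is applied to the outcome models.

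**What to change.** 1. Delete the exclusion sentence in C3, Treatment Integrity, and the matching data-exclusion sentence in C2, Therapist training procedures, as rules for the main analyses. Changing only the first would leave the therapist rule cutting the same low end. The plan to replace a therapist is a separate matter and is not affected.
2. State that every randomized woman stays in the intent-to-treat analyses, whatever her adherence and competence ratings.
3. Run the adherence and competence correlations on all rated cases, one value per woman (for example the mean of her rated sessions), within arm, with confidence intervals.
4. If an analysis without inadequately delivered cases is wanted, label it a sensitivity analysis and state that it covers only women with a rated session.

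**Cost.** A few sentences of text, with no new data or participants. The one downside is that the intent-to-treat estimate will include some poorly delivered treatment; the sensitivity analysis can show how much that matters among the rated cases.
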